In Philadelphia, children ≤36 months of age with ASD are eligible for treatment through the infant and toddler early intervention program. Risk is determined using the Modified Checklist for Autism in Toddlers. Thirteen agencies provide these services. They use an interdisciplinary treatment approach, have a treatment philosophy that supports parent-mediated intervention, and provide home-based services. The early intervention system projects that >800 children with autism ≤36 months of age will receive services next year. On average, children receive 3.4 hours/week of services, about one hour of which comprises "specialized instruction," which Project ImPACT will replace. Children will retain all other services. In specialized instruction, therapists: 1) design learning environments and activities that promote skill acquisition; 2) plan activities that address the outcomes on the individualized family service plan; 3) provide families with information, skills and support to enhance child skill development; and 4) work with the child and family to enhance the child's development. Specialized instructors typically are bachelors-prepared individuals with early child development training.

Aim 1: Compare outcomes in young children (social communication and development) and their parents (stress and self-efficacy) randomized to one of three groups: A) treatment as usual, B) Project ImPACT delivered at 1 hour/week and C) Project ImPACT delivered at 4 hours/week.

Overview

We will compare the outcomes of young children and their parents randomized to three groups: A) treatment as usual, B) 6 months of Project ImPACT at 1 hour/week and C) 6 months of Project ImPACT at 4 hours/week. Observations of regular early intervention sessions between families and clinicians will provide evidence of adherence to the Project ImPACT intervention. Observations of parent and child interactions as well as direct assessments with enrolled children over the course of 6 months, will give information on changes in social communication and parent responsiveness and self-efficacy.

Sample

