Clinician Fidelity will be measured using the Project ImPACT Coaching Fidelity Checklist.¹ Clinicians assigned to the two active treatment groups will self-monitor their coaching fidelity as part of the implementation procedure. We also will observe clinicians monthly to ensure accurate self-monitoring in the active treatment groups and to capture the extent to which clinicians in the treatment as usual group use any elements of ImPACT. Previous research indicates high interrater reliability between self and observer ratings on the coaching fidelity form (99% exact agreement);⁴² thus we anticipate that self-ratings will provide an accurate measure of clinician behavior.

Cluster Randomized Study Design

Six agencies will be blocked into groups of 3 based on agency size and location. Within each group of three, each agency will be randomized to one of three conditions: 1) treatment as usual; 2) ImPACT at a dose of 1 hour/week over 6 months; and 3) ImPACT at 4 hours/week over 6 months.

Statistical Analysis for Aim 1

Outcomes will be analyzed as continuous variables at the child or parent level across time. Initially all outcomes will be described using summary statistics (means, medians, and estimates of variance). The longitudinal nested random effects linear models will be used for each outcome; the models will consist of three levels of random effects to adjust for individual child/parent, agency and clinician variability. For each measure, the analysis dataset will contain one observation with each subject's outcome measure at baseline and follow-up. The dependent variable in each model will be the measure of outcome at each time point. The independent variables will include a categorical variable for time period (baseline, 3 months, or 6 months), group (ImPACT_1hr/wk, ImPACT_4hr/wk or comparison), and their interaction. The magnitude and statistical significance of the beta coefficient for the interaction will provide an intent-to-treat assessment of the extent to which the intervention group improved relative to the comparison

group. Because agencies are randomly assigned, we expect clinicians and children in our intervention and comparison groups to be similar across baseline characteristics; however, if we find between-group differences we will control for them in our regression models.

Aim 2: Examine the cost effectiveness of Project ImPACT at different doses.

Overview

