The purpose of the cost evaluation is to determine both the cost of implementing Project ImPACT in Philadelphia, and the cost associated with any additional benefit of one treatment arm over the other. Both questions are of great interest to our community partners and system administrators in general. Our cost-effectiveness analysis will take two perspectives: 1) a service perspective, which is of particular interest to policy makers and includes hospital, community and school-based health, social and education services; and 2) a societal perspective to capture the full economic implications, which also include parental out-of-pocket costs (insurance copayments, unreimbursed therapies and materials etc.), child care and schooling costs, productivity losses (time off work due to child's condition), and unpaid care.

Measures

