
capital approach, which involves multiplying time off work by the parent's wage rate.⁵⁰ We will calculate informal care costs using the market price approach that applies the price that would be paid if the care were provided by a formal care giver.⁵¹ Finally, we will calculate total costs for each agency and then averaged across centers within each study arm to determine average costs per study condition.

Data Analysis

The outcomes of different study arms will be combined with their respective costs to provide a measure of relative cost-effectiveness that can be compared to other interventions employing the same measure of outcome. The effects will be improvements in child and parent outcomes. Using the estimated mean cost and mean effect per patient by intervention group, we will construct an incremental cost-effectiveness ratio for each outcome for which Project ImPACT shows a significant effect. Incremental cost-effectiveness will be computed as the ratio of the difference in mean costs (incremental cost) to the difference in mean effects (incremental effect), and will represent the additional cost per additional improvement in child development and social communication scores and parent stress and self-efficacy scores, of one intervention arm compared to another. A joint distribution of incremental mean costs and effects for the intervention arms being compared will be generated using non-parametric bootstrapping.⁵² We will use these data to explore the probability that each treatment is optimal choice, subject to a range of possible maximum values (ceiling ratio) that a decision maker might be willing to pay for an additional improvement in child or parent outcome score. Cost-effectiveness acceptability curves (CEAC) will be generated by plotting these probabilities for a range of possible values of ceiling ratios. 53,54 CEACs are a standard decision-making approach to dealing with the uncertainty around the estimates of expected costs and effects and uncertainty regarding the maximum CER a decision maker would consider acceptable.⁵⁴ We will examine baseline characteristics across intervention groups to determine whether randomization was successful in balancing observed baseline covariates. If there is unbalanced allocation in baseline characteristics, we will use net-benefit regression to estimate directly in a regression framework.

Statistical Power

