We base our statistical power analysis upon Aim 1, our primary aim, which tests the effects of Project ImPACT on child and parent outcomes. Prior studies of Project ImPACT and related parent-mediated interventions indi-cate a large effect on parent treatment adherence (.90-1.30), and a moderate effect on child outcomes (.34-.70).16,19,42 Meta-analytic reviews of studies of parent-implemented interventions for children with ASD report effects of .8 to 1.1.26 We used Power and Precision software, and assumed an alpha of 0.05, and that all tests are 2-tailed. We will have enrolled 3 clinicians in each agency and 3 children per clinician (18 subjects per intervention group). Due to statistical software limitations in addressing multiple levels of clustering in power estima-tion, we adopted two perspectives. First, we explored potential effect sizes (Cohen's d) with nesting of clinicians within agencies. Second, we estimated potential effect sizes with nesting of patients within clinicians. We as-sume an intra-class correlation of 0.05. In the first case, we calculate that we will have power of 80% to detect a moderate intervention effect of d=0.66. In the second case, we calculate that we will have power of 80% to de-tect a moderate intervention effect of d=0.53.

PROTECTION OF HUMAN SUBJECTS

Research will not begin until the Institutional Review Boards of the University of Pennsylvania and the City of Philadelphia approve the proposed study.

Characteristics of Population

We anticipate the sample of parent-child dyads will be 45% African American, 26% Latino, 18% Caucasian, 6% Asian, 2% American Indian/Native American, and 3% multi-racial. Children will be less than 3 years of age, and will either have a diagnosis of autism spectrum disorder or be identified as at-risk for autism by the early intervention system, as children under three years of age do not need a formal diagnosis to receive autism-specific treatment. We anticipate that 75% of the children will be male based on the sex distribution of autism. Participants will be excluded if they do not speak English. This is due to the procedures of the project, which include coding of videos of early intervention sessions. The team currently does not have capacity to code videos that are not in English. Participants will not be excluded based on their gender or past experience.

Data to be collected from Human Subjects

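### Aim 2 computes a cost-effectiveness ratio only for outcomes with a significant effect, which leaves the others without one and tends to make the reported cost per unit gain too low

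*Combined protocol and SAP*

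**What the plan says.** Aim 2, Data Analysis, defines the incremental cost-effectiveness ratio (ICER) as the difference in mean costs divided by the difference in mean effects between two arms. It then limits its use: "we will construct an incremental cost-effectiveness ratio for each outcome for which Project ImPACT shows a significant effect". No substitute is named for outcomes that fail this condition.

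The same section plans for uncertainty: "A joint distribution of incremental mean costs and effects for the intervention arms being compared will be generated using non-parametric bootstrapping". Acceptability curves (CEACs) follow, with the explanation that "CEACs are a standard decision-making approach to dealing with the uncertainty around the estimates of expected costs and effects". Neither sentence repeats the significance condition, and neither says that it is lifted.

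The Overview of Aim 2 gives the purpose as finding the cost of implementation and "the cost associated with any additional benefit of one treatment arm over the other".

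The significance in question presumably comes from Aim 1. There the group-by-time interaction gives an "intent-to-treat assessment of the extent to which the intervention group improved relative to the comparison" group.

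**The concern.** The effect estimate that decides whether an outcome gets an ICER is also the denominator of that ICER. Selecting on significance keeps the trials in which the estimate came out high. With a true benefit and a positive incremental cost, a denominator that is too large makes cost per unit gain look too low. Outcomes that miss significance disappear from the ICER table, although their costs and effects have been estimated.

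This fits poorly with the rest of Aim 2. The stated purpose concerns any additional benefit, not only significant benefit. The bootstrap and CEAC already carry the uncertainty that a p-value condition would be meant to guard against.

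The Abstract calls the relative benefit at different doses critically important to the community partners. If ICERs for child outcomes appear only when the estimate happens to be high, the system's funders see figures that lean towards ImPACT.

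**Working it through.** **Inputs (Statistical Power section).** Two-sided alpha 0.05; 18 children per arm; intra-class correlation 0.05; expected child effects d = .34 to .70; expected parent-adherence effects .90 to 1.30; 80% power claimed at d = .66 and d = .53. From the design: 3 clinicians × 3 children = 9 children per agency.

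**The plan's own power figures.** The detectable d at 80% power is (1.96 + 0.84) × SE, with SE = √(2/18 × DE) for an endpoint comparison of 18 with 18.
- DE = 1.0: SE = .333, detectable d = 2.80 × .333 = .93.
- DE = 1 + (9 − 1) × 0.05 = 1.4: SE = .394, detectable d = 2.80 × .394 = 1.10.

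These do not reproduce .66 or .53. Strong baseline adjustment could close the gap, but no baseline correlation is stated. That is a separate matter, so two precision cases are carried forward:
- Stated power accepted: SE = .66/2.80 = .236 and .53/2.80 = .189.
- Endpoint comparison, 18 per arm: SE = .333 to .394.

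**Model.** Each ImPACT-versus-usual-care estimate is Normal(d, SE). Both ImPACT arms have the same true d and share one usual-care arm, so the two contrasts have correlation 0.5. Following the per-outcome wording, an outcome qualifies if either contrast is significant in the direction of benefit (estimate > 1.96 × SE). Inflation is the mean estimate among qualifying outcomes divided by d (1,500,000 simulated trials).

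| True d | Stated power: no ICER | Stated power: inflation | 18 per arm: no ICER | 18 per arm: inflation |
|---|---|---|---|---|
| .34 | 40–55% | 1.3–1.5 | 72–78% | 2.0–2.3 |
| .53 | 9–23% | 1.05–1.14 | 49–60% | 1.4–1.6 |
| .70 | 1–6% | 1.01–1.04 | 28–41% | 1.2–1.3 |

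For parent adherence with 18 per arm, d = .90 gives no ICER in 11–22% of trials and inflation of 1.06–1.14. At d = 1.30 inflation is at most 1.06, which is near nil.

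**A check by hand, one contrast only.** Take d = .34 and SE = .236.
- Chance of no ICER: Φ(1.96 − .34/.236) = Φ(.52) = .70.
- Inflation: 1 + (.236/.34) × φ(.52)/(1 − .70) = 1 + .694 × 1.15 = 1.80.

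Allowing either of two contrasts to qualify the outcome brings these down to 55% and 1.5.

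**Effect on the ratio.** With incremental cost held fixed and positive, inflation by a factor f gives a ratio of roughly 1/f of the truth. At d = .34 that is 1/1.5 = .67 to 1/1.3 = .77 with stated power, and 1/2.3 = .43 to 1/2.0 = .50 with 18 per arm.

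**Sensitivity to the model.** The endpoint SE equals that of a change score only at a baseline correlation of 0.5. With an assumed correlation of 0.8 and DE 1.4, SE = .394 × √(2 × 0.2) = .249. Inflation is then 1.57, 1.18 and 1.05 at d = .34, .53 and .70, with no ICER in 59%, 27% and 9% of trials.

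**Without the condition.** The effect estimate is not selected, so inflation is 1.00 and every named outcome is reported. If trials with a zero or negative effect are ranked as the worst results, the median ICER equals the truth.

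**The case against.** The strongest defence is that a ratio with a denominator near zero is unstable or meaningless, so declining to print one is reasonable. It is also true that the bootstrap and CEAC sentences carry no condition. Aim 1 models every outcome, and Aim 2 computes average costs per condition. A reader might infer that non-significant outcomes get no economic evaluation at all, but the documents do not support that. What is clearly withheld is the ratio; coverage by the bootstrap and CEAC is unstated. This narrows the point without removing it, since the selected ratios are still reported as they stand.

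Four other stronger readings also go beyond the documents.
- **That the bias is large everywhere.** The larger figures come from an endpoint comparison, whereas Aim 1 specifies a longitudinal model. With the stated power accepted, inflation is modest at d = .53 and slight at d = .70. The Statistical Power section also cites meta-analytic effects of .8 to 1.1, where it is small.
- **That each contrast must be significant by itself.** The ICER compares one arm with another, so this reading is possible, and it gives larger figures (57–70% without an ICER and 1.5–1.8 times inflation at d = .34 with stated power). The sentence is worded per outcome, so the looser reading is used here.
- **That the 4 h versus 1 h ratio is biased by these amounts.** The figures concern ImPACT versus usual care. With equal effects in both ImPACT arms, the true difference between doses is zero, its ratio is undefined, and the condition adds no bias to the mean difference. The dose contrast with unequal effects is not quantified here.
- **That the ratio would be too low even without the condition.** That follows only if negative-effect results (15–19% of trials at d = .34 with 18 per arm) are counted as cheap. With a positive cost they are dominated.

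**Conclusion.** The point holds. The plan makes the ICER conditional on significance, no other section lifts this, and the screened effect is the denominator. Non-significant outcomes get no ratio, and reported ratios tend to be too low. The bias matters most for child outcomes near the low end of the protocol's expected range and is negligible for large effects.

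The direction rests on a true benefit and a positive incremental cost. The documents give no cost totals. The Setting section says that about one hour a week of existing specialized instruction is the part "which Project ImPACT will replace. Children will retain all other services", so the sign of the incremental cost cannot be taken as known, particularly in the 1 h arm. The sizes also assume equal effects in both ImPACT arms and normally distributed estimates, and they depend on which precision is believed. Confidence is therefore medium. This is a cheap improvement to Aim 2, which is not the aim on which the study is powered.

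**What to change.** Delete the words that restrict the ICER to outcomes with a significant effect. Name the outcomes before analysis, and cover all three contrasts: 1 h versus usual care, 4 h versus usual care, and 4 h versus 1 h. For each, whatever the p-value, report incremental cost, incremental effect with its interval, the bootstrap joint distribution, and the CEAC or net benefit. State that the bootstrap and CEAC cover every named outcome and contrast.

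Make net benefit and the CEAC the main summary for every outcome, significant or not. Show the point ICER alongside, marked as dominated or undefined where the effect is zero or negative. The summary should not switch according to whether the effect interval includes zero, because that would bring the significance condition back.

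The cost is a change of wording and some further analyses of data already collected, with no new visits or participants. The report will be longer, and some of the ratios will be very imprecise.

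### The two 80% power figures (d=0.66 and d=0.53) do not follow from the stated inputs: 18 children per arm gives d=0.96 before any clustering

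*Combined protocol and SAP*

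**What the plan says.** The Statistical Power section bases its calculation on Aim 1, which it calls the primary aim. It assumes two-tailed tests at alpha 0.05, an "intra-class correlation of 0.05", and a sample of "3 clinicians in each agency and 3 children per clinician (18 subjects per intervention group"). Because the software could not handle several levels of clustering, it takes two views one at a time. The first is "with nesting of clinicians within agencies"; the second is children within clinicians. The results are: "In the first case, we calculate that we will have power of 80% to detect a moderate intervention effect of d=0.66", and 80% power for d=0.53 in the second case.

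For context the section cites "a large effect on parent treatment adherence (.90-1.30"), "a moderate effect on child outcomes (.34-.70") and meta-analytic effects of .8 to 1.1.

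Under Cluster Randomized Study Design, "Six agencies will be blocked into groups of 3 based on agency size and location", and each agency in a block goes to one of three arms, so there are two agencies per arm. Statistical Analysis for Aim 1 plans a longitudinal mixed model with a time-by-group interaction. Neither section gives a baseline/follow-up correlation, a covariate R-squared, the contrast that was powered, or degrees of freedom.

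**The concern.** With 18 per arm, a two-group comparison at conventional alpha and power detects an effect close to one standard deviation. Clustering makes that worse. Detectable effects of 0.66 and 0.53 are far below what these inputs allow, so either an input was left out or the figures are mistaken.

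The figures matter because they make the trial appear adequately powered for the upper part of the child-effect range the plan expects. If true power is well below 80%, a null child result could be read as evidence of no effect. Aim 2 is also exposed, because its Data Analysis section builds cost-effectiveness ratios only for outcomes with a significant effect. The Abstract says the findings will be the basis of an application for federal funds.

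**Working it through.** **Inputs from the plan.** 18 children per arm; 2 agencies per arm (6 agencies, 3 arms); 9 children per agency; 3 children per clinician; ICC 0.05; two-sided alpha 0.05; power 80%.

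**Formulas.** Design effect DE = 1 + (m − 1) × 0.05. In SD units, SE = √(DE × (1/18 + 1/18)). Detectable d = K × SE, where K is the noncentrality that gives 80% power. K is 2.802 (normal), 2.884 (t, 34 df), 3.110 (10 df), 4.256 (3 df) and 5.65 (2 df). The first case is read here as m = 9 children per agency, so DE = 1.4. The second is m = 3 children per clinician, so DE = 1.1.

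**Attempt to reproduce 0.66 and 0.53, with no gain from baseline:**

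| Setting | SE | Normal | 34 df | Cluster df |
|---|---|---|---|---|
| Independent | 0.333 | 0.93 | 0.96 | – |
| DE 1.1 (clinician) | 0.350 | 0.98 | 1.01 | 1.09 (10 df) |
| DE 1.4 (agency) | 0.394 | 1.10 | 1.14 | 1.68 (3 df); 2.23 (2 df) |

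Agency df is 6 agencies − 3 arms = 3, or 2 once the blocks are removed. Neither stated figure appears.

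**Sample size the stated figures imply.** n per arm = 2 × (K/d)². With the normal K, 2 × (2.802/0.66)² = 36.0, which rounds up to 37, and 2 × (2.802/0.53)² = 55.9, which rounds up to 56. By exact t, the numbers are 38 and 57 independent children per arm.

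**Power actually available (noncentral t).**

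| d | Independent | DE 1.4, 34 df | DE 1.4, 3 df |
|---|---|---|---|
| 0.34 | 17% | 13% | 10% |
| 0.53 | 34% | 26% | 16% |
| 0.66 | 49% | 37% | 22% |
| 0.70 | 53% | 41% | 24% |
| 0.90 | 75% | 60% | 35% |
| 1.30 | 97% | 89% | 61% |

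**Other readings tried.**
- Both ImPACT arms pooled against usual care (36 v 18), unclustered: 0.82.
- One-sided test: 0.83 (normal) or 0.85 (t), although the plan says two-tailed.
- 54 per group in place of 18 (normal): 0.64 with DE 1.4 and 0.57 with DE 1.1.
- First case taken literally, with 6 clinicians per arm as units in clusters of 3: about 1.70 (normal), in clinician-level SDs.

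**Could a baseline correlation r explain the figures?** ANCOVA multiplies the SE by √(1 − r²), and a change score multiplies it by √(2(1 − r)). All values of r here are assumptions, since the plan gives none.
- Without clustering, 0.66 needs r of 0.73 (ANCOVA) or 0.76 (change), and 0.53 needs 0.83 or 0.85.
- With the stated ICC on 34 df (ANCOVA), 0.66 at DE 1.4 needs √(1 − (0.66/1.137)²) = 0.81. For 0.53 at DE 1.1, the value is √(1 − (0.53/1.008)²) = 0.85.
- On 3 agency df at DE 1.4, 0.66 needs about 0.92 and 0.53 about 0.95.

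For a range of r (ANCOVA, DE 1.4), the detectable d on normal / 34 df / 3 df is 0.96 / 0.99 / 1.45 at r = 0.5, 0.79 / 0.81 / 1.20 at r = 0.7, and 0.66 / 0.68 / 1.01 at r = 0.8.

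**Consistency of the pair.** A common r cancels from the ratio of the two figures. The stated ratio is 0.66/0.53 = 1.25. The two design effects imply √(1.4/1.1) = 1.13 on a common df. Cluster df of 3 and 10 imply 1.68/1.09 = 1.54. On these readings, no single r gives both figures.

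**The case against.** The strongest reply is that the planned model uses baseline data, so a calculation that ignores baseline is not the one the trial needs. The software run is not visible, and the figures are not impossible under a baseline-adjusted analysis. That stands, and it is why the finding is that the figures do not follow from the stated inputs, rather than that no calculation could produce them.

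The reply is stronger for parent outcomes, which are measured at baseline, 3 and 6 months. If the contrast averages both follow-ups, with equal correlations and adjustment for baseline, the variance factor is (1 + r)/2 − r². The required r then falls to about 0.725 for 0.66 (DE 1.4) and 0.785 for 0.53 (DE 1.1), on 34 df. These are still two different, unstated values. The variant does not help child outcomes, which have no 3-month measurement.

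Several smaller points also stand:
- Reading the first case as nine children per agency is an interpretation, and the ratio check depends on it. The 0.96 floor does not.
- The plan states no df, so the 3 df results are scenarios and not consequences of stated inputs.
- Two agencies per arm can be worked out within the power section: 18/(3 × 3) = 2.
- The cited meta-analytic effects of .8 to 1.1 are more favourable than the child range. At DE 1.4 on 34 df they have about 50% to 77% power, still below 80%.

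The trial is called a pilot, and nothing says its size was derived from this calculation. That limits the practical consequence, but the plan still claims 80% power for specific effects.

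**Conclusion.** The concern holds. On the stated sample size, alpha and power, the pairwise detectable effect is 0.96 for independent children. With the stated ICC on 34 df it is about 1.01 or 1.14. Both published figures lie below that floor and would need roughly two to three times the planned children per arm. The floor assumes only a two-arm comparison with no gain from baseline.

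If a baseline correlation was used, it is the decisive input and is missing. If none was used, the figures are wrong. The section has to change in either case.

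The overstatement falls mainly on child outcomes. With agency clustering and no baseline gain, power over .34–.70 is about 13% to 41% on 34 df, or 10% to 24% on 3 agency df. For parent adherence (.90–1.30) it is about 60% to 89%, or 35% to 61%. A real baseline correlation would raise all of these; its size is unknown from the documents.

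**What to change.** Replace the two figures in Statistical Power with recomputed ones. State the comparison (pairwise or pooled), children and agencies per arm, the design effect in each case, the df method, and any assumed baseline/follow-up correlation.

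- If no correlation was used, report a detectable effect of about 1.1 SD (large-sample) and about 1.7 SD or more on agency-level df. Say that power for child effects of .34–.70 is well below 80%.
- If a correlation was used, give its value and source, say how many follow-ups enter the contrast, and report the detectable effect on both large-sample and agency-level df.

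In both cases report power separately for the child and parent-adherence ranges, because the number of measurements and the expected effects differ.

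The cost is one recomputed and reworded paragraph, with no change to enrolment. The drawback is a less favourable stated figure.
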